4.0 TRIAL OVERVIEW

4.1 Study Design

4.1.1 Introduction

This is a Phase I/II, non-randomized, open-label, interventional study of avelumab combined with trabectedin for subjects with advanced L-type sarcoma.

The Phase I stage will evaluate trabectedin (1.5 mg/m²) combined with avelumab (800 mg flat dose). Dose reduction for the trabectedin therapy is permitted after the first cycle. Events which would require a dose reduction of trabectedin are outlined in Section 10, however additional dose reductions may be made at the discretion of the treating clinician down to a lowest possible dose of 1 mg/m². There will be no dose escalation or re-escalation of trabectedin.

4.1.2 Definition of dose limiting toxicity (DLT):

During the phase I portion of the protocol, a DLT will be defined as any grade 3 or higher adverse events, at least possibly-related to protocol therapy, which occur during the first 6 weeks of treatment, with the following specifications and limitations:

- Lab abnormalities that have no clinical sequelae (e.g. febrile neutropenia from low ANC, bleeding from thrombocytopenias etc.) and resolve to grade 1 or better within 7 days will not be considered a DLT.
- Any elevation in total bilirubin > 2x institutional ULN will be considered a DLT.
- Any elevation in AST and ALT over 8x institutional ULN will be considered a DLT.
- ANC <500/ μ L lasting 5 days or more will be considered a DLT.
- Platelets < 25,000/ μ L (grade 4 toxicity) lasting 5 days or more will be considered a DLT.
- Hemoglobin < 7.0 lasting 5 days or more will be considered a DLT.

Additionally, should any grade 5 toxicity (death) occur that is at least possibly-related to treatment (e.g. not easily otherwise explained; for example: a car accident), this will be considered a DLT. In the event of any grade 5 toxicity, enrollment will immediately be put on hold and a data safety monitoring board (DSMB) meeting will be requested immediately.

All clinically significant grade 3 or higher toxicities will be recorded and presented to the DSMB at scheduled meetings. Expected toxicities are those outlined in [Section 10](#). The DSMB will be specifically instructed to consider whether there are increased frequency of known toxicities and to make recommendations accordingly if appropriate. Section 10 summarizes criteria for required dose adjustments.

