9.6 Attribution of an Adverse Event

Association or relatedness to the study agent will be assessed by the investigator as follows:

- **Definite:** The event follows a reasonable temporal sequence from exposure to the investigational agent, has been previously described in association with the investigational agent, and cannot reasonably be attributed to other factors such as the subject's clinical state, other therapeutic interventions or concomitant medications; AND the event disappears or improves with withdrawal of the investigational agent and/or re-appears on re-exposure (e.g., in the event of an infusion reaction).
- **Probable:** The event follows a reasonable temporal sequence from exposure to the investigational agent and has been previously been described in association with the investigational agent OR cannot reasonably be attributed to other factors such as the subject's clinical state, other therapeutic interventions or concomitant medications.
- **Possible:** The event follows a reasonable temporal sequence from exposure to the investigational agent, but could be attributable to other factors such as the subject's clinical state, other therapeutic interventions or concomitant medications.
- **Unlikely:** Toxicity is doubtfully related to the investigational agent(s). The event may be attributable to other factors such as the subject's clinical state, other therapeutic interventions or concomitant medications.
- **Unrelated:** The event is clearly related to other factors such as the subject's clinical state, other therapeutic interventions or concomitant medications.

For general AE assessment, an AE is considered related if it is assessed as definitely or probably related; unrelated if it is assessed as possibly, unlikely related or unrelated.

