10.3 Toxicity of Trabectedin

Trabectedin is given as standard of care and does have notable toxicities. The following are to be considered expected toxicities of trabectedin:

- Leukopenia (with neutropenia as the predominant component)
- Malaise
- Infection/sepsis
- Transaminase Elevation
- CK elevation
- Bilirubin or Alkaline phosphatase elevation
- Fatigue
- Nausea/vomiting
- Renal toxicity

Rhabdomyolysis is an unusual but well-described toxicity of trabectedin. If rhabdomyolysis is observed in a single case, this should not be considered a DLT but if multiple cases are seen, this must be reviewed by the DSMB.

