16.2 Phase I Design

The primary objective of the Phase I component of this study is to evaluate the safety of avelumab given in combination with trabectedin among subjects with advanced L-type sarcomas. The phase I component of this study will treat 6 subjects (modified 3+3 design) to demonstrate safety of the combination. Dose-limiting toxicities will be defined as unexpected, probably-related toxicities of grade 3 or higher.

The study design is as follows:

6 subjects will be treated initially.

- If 2 or more subjects experience a DLT at any point during the Phase 1 portion, a new cohort will be added, enrolling an additional 6 subjects at a reduced dose of 1 mg/m² trabectedin.
- Should 2 or more of these next 6 subjects at the reduced dose have a DLT, stop and convene DSMB meeting to recommend changes to the protocol.
- If at any time in the study (including those above) 30% of subjects have a DLT, have a DSMB meeting to review specific toxicities. We will re-calculate the percent of subjects who have had a DLT each time there is a new DLT.

If <2 subjects have DLTs on the 1 mg/m² dose level, another Phase I cohort of 6 subjects implemented, re-escalating to 1.2 mg/m² dosing of trabectedin. If <2 DLTs are seen there, that will be the recommended Phase II dose. If 2 or greater DLTs are seen there, the Phase 2 will move forward at the 1.0 mg/m² dose level, after discussion with the DSMB.

Safety analysis will continue through the entire trial, if at any point during the trial 30% of subjects experience a DLT, the trial should halt and convene a meeting of the DSMB.

A total of up to 18 subjects may enroll on Phase 1, and an additional 16 on Phase 2.

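### DLT has two incompatible definitions (4.1.2 and 16.2) for the same 2-of-6 dose rule, and neither is set for Phase 2

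*Combined protocol and SAP*

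**What the plan says.** **Definition in 4.1.2.** The section opens with severity: "During the phase I portion of the protocol, a DLT will be defined as any grade 3 or higher adverse events". Attribution and timing then narrow this to events that are "at least possibly-related to protocol therapy, which occur during the first 6 weeks of treatment". The bullets that follow exempt laboratory abnormalities that have no clinical sequelae and resolve to grade 1 or better within 7 days. They then name specific DLTs, among them total bilirubin above 2x ULN and this one: "Any elevation in AST and ALT over 8x institutional ULN will be considered a DLT". Expected events are not excluded.

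**Definition in 16.2.** "Dose-limiting toxicities will be defined as unexpected, probably-related toxicities of grade 3 or higher". DLTs are counted at any point in the Phase 1 portion. There is no 6-week window and there are no laboratory rules.

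**The dose rule.** Both sections apply the same rule: 2 or more DLTs in the first 6 subjects lowers the starting trabectedin dose from 1.5 to 1.0 mg/m², with later cohorts decided in the same way.

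**Expectedness and relatedness.** Section 4.1.2 says "Expected toxicities are those outlined in" Section 10. Section 10.3 begins its list with "The following are to be considered expected toxicities of trabectedin" and includes "Transaminase Elevation" as well as bilirubin elevation. For general assessment, 9.6 treats an event as "unrelated if it is assessed as possibly, unlikely related or unrelated".

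**The 30% trigger.**
- 16.1 halts accrual above 30%, with no minimum number of subjects.
- 16.2 calls a DSMB meeting, and halts the trial, at 30%, at any time and expressly including the first cohorts. The percentage is recalculated at each new DLT.
- 16.4 has the DSMB meet at 2 of the first 6, and after that above 30%, naming the three dose levels.
- 4.1.2 has its own Phase 2 hold, based on unexpected, probably related SAEs of grade 3 or higher that do not resolve to grade 2 within 2 weeks.

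**The concern.** The two definitions differ in relatedness, expectedness, time window and laboratory thresholds. If they classify the same event differently, two teams following the same protocol could choose different Phase 2 doses from identical data. Safety is a primary endpoint. Under 16.3, the efficacy set includes only those Phase 1 subjects treated at the dose finally chosen, so the choice affects both halves of the trial.

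Liver toxicity is where the difference is easiest to foresee. Section 2.6 reports liver-function abnormalities as the DLTs at 1.5 mg/m² in the Japanese phase I trial, and grade 3/4 AST and ALT in about half of the subjects in one phase II trial of trabectedin alone.

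The second issue is reach. Section 4.1.2 limits its definition to Phase I, and the other definition stands under the heading Phase I Design. Yet 16.1, 16.2 and 16.4 count DLTs through the whole trial.

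**Working it through.** **1. The plan's own figures.** The plan gives no operating characteristics for the DLT rules, so there is nothing to reproduce on this point. The only stated figure is 85% power for response (22 subjects, 6 or more responses, 9.9% against 35%). The exact binomial gives 83.7%, which is close, and nothing below depends on it.

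**2. The two definitions applied to the same events**

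| Event in a Phase 1 subject | 4.1.2 | 16.2 |
|---|---|---|
| Grade 3 clinical event, week 3, possibly related | DLT | Not a DLT: not probably related |
| AST and ALT over 8x ULN, week 3, not resolved within 7 days | DLT | Can fail: listed as expected in 10.3 |
| Bilirubin 2-3x ULN, week 3, not resolved within 7 days | DLT | Not a DLT: grade 2 in the hepatic table of 10.2.2.4 (above 1.5 to 3x ULN) |
| Unexpected, probably related grade 3 event, week 8 | Not a DLT: outside 6 weeks | DLT |

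The first three rows count only under 4.1.2, or can do so; the last counts only under 16.2. The definitions are therefore not nested, and 16.2 cannot be read as a summary of 4.1.2.

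**3. Effect on the dose rule.** With per-subject DLT rate p (assumed, since the documents give none for the combination):

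P(2 or more of 6) = 1 − (1 − p)^6 − 6p(1 − p)^5

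- p = 5%: 1 − 0.7351 − 0.2321 = 3.3%
- p = 10%: 1 − 0.5314 − 0.3543 = 11.4%
- p = 20%: 1 − 0.2621 − 0.3932 = 34.5%
- p = 30%: 1 − 0.1176 − 0.3025 = 58.0%

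If the two definitions gave rates of 10% and 30%, for illustration only, the chance of de-escalation would be 11% under one and 58% under the other.

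**4. The 30% trigger (secondary).** Take the denominator as subjects treated so far, which is an inference from the recalculation sentence in 16.2, and assume that each DLT is known at once. One DLT among the first 1, 2 or 3 subjects is then 100%, 50% or 33%. That triggers both 16.1 and 16.2 but nothing under 16.4. At p = 10%, P(at least one DLT in the first 3) = 1 − 0.9³ = 27.1%.

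An exact subject-by-subject recursion to n = 22, at one dose level and with the fraction checked at each new DLT, gives the probability of at least one trigger:

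| Assumed rate | 16.1 (above 30%) | 16.2 (30% or more) | 16.4 (2 of first 6, then above 30%) |
|---|---|---|---|
| 5% | 15.0% | 15.1% | 3.5% |
| 10% | 30.2% | 30.7% | 13.4% |
| 20% | 60.6% | 61.8% | 45.6% |

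The figures for 16.1 and 16.2 are upper-end values. If two further subjects have started by the time each DLT is known, the 16.1 figure at a 10% rate falls from 30.2% to 13.9%. The difference between 30% and more than 30% matters only at n = 10, 20 and 30.

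**The case against.** **Expected does not always mean excluded.** Section 9.3 makes unexpectedness depend on severity and frequency as well as nature, so an unusually severe transaminase rise might still count under 16.2. This stands, and it is why the AST/ALT row says only that the event can fail. It does not touch the differences in relatedness, window and bilirubin.

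**The liver rate is not a DLT rate.** A reader might infer from the figure of about half in 2.6 that 4.1.2 would almost always force de-escalation. The documents do not support that. The figure is for trabectedin alone, covers the whole treatment course, and concerns grade 3/4 rather than the 8x ULN threshold within 6 weeks. It shows that the conflict is relevant, not how large it is.

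**The hold rules conflict less than they seem to.** A reader might infer that three sections give contradictory stopping rules and that the denominator is missing. In fact 16.4 states when the DSMB meets and contains no halt, so the last table sets halts beside a meeting trigger. Its mention of the three doses can be read as a per-dose denominator, so the text is ambiguous rather than silent. A trigger leads to a temporary review, and the DSMB Charter cited in 16.1, which is not available here, may settle the timing. The wording in 16.2 also suggests that early triggers were intended. All of this stands, and it makes the trigger secondary.

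**Later cohorts.** A reader might also infer that DLTs carried over from the first cohort would often halt the second. Section 4.1.2 lets subjects in later cohorts be treated concurrently, so that would depend on enrolment timing the plan does not fix, and no size can be given.

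**Conclusion.** The definition conflict is real and sits in current text. Sections 4.1.2 and 16.2 give non-nested definitions for one dose rule, with no precedence stated, and neither reaches Phase 2. The recommended Phase 2 dose can therefore depend on which section the team follows.

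The size is conditional: between assumed DLT rates of 5% and 30%, the chance of de-escalation runs from 3.3% to 58.0%. The documents do not say which rate either definition would produce, so they do not show that a wrong dose would be chosen, only that the choice is not determined.

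The 30% trigger is inconsistently worded. At a 10% rate the chance of a trigger by 22 subjects is about 30% under 16.1 and 16.2 against 13% under 16.4, on the assumptions of a treated-so-far denominator and immediate readout. This should be corrected, but it governs a review and not a dose.

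**What to change.** **Dose decision.**
- Make 4.1.2 the only DLT definition, and replace the sentence in 16.2 with a cross-reference.
- State whether the AST/ALT and bilirubin bullets override the 7-day laboratory exception or the reverse. At present a rise above 8x ULN that resolves within 7 days is both exempted and included.
- Carry over from 10.3 the provision that a single case of rhabdomyolysis is not a DLT.

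**Trial-wide 30% rule.**
- Use the same event criteria in both phases, but without the 6-week cap. Sections 8.5 and 9.7.1 stress delayed immune-related toxicity, and 16.2 intends monitoring throughout the trial.
- State the rule once in 16.4 and cross-refer from 16.1 and 16.2: one threshold (more than 30%), one denominator (subjects treated at that dose), one action (accrual halts until DSMB review).
- Say explicitly whether it applies before the 7th subject at a dose. If it starts there, the limits are 3 DLTs among 7-9 subjects, 4 among 10-13, 5 among 14-16, 6 among 17-19 and 7 among 20-22.
- Label the Phase 2 SAE hold in 4.1.2 as a separate rule.

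**Cost.** The change is wording in 4.1.2, 16.1, 16.2 and 16.4, and in the DSMB Charter where it repeats them. Section 4.1.2 counts more events in the first 6 weeks, so de-escalation is more likely than under 16.2. The team must keep two counts, one within 6 weeks and one without a cap. Starting the 30% rule at the 7th subject gives up an automatic halt after one early DLT; the staggered first cohort, the grade 5 hold and DSMB review of Phase I DLTs cover this in part. Under Appendix C, Phase 2 subjects need no visit in weeks without treatment, so laboratory DLTs defined by duration will be captured less completely there.

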16.3 Phase II Design

The primary objective of the Phase II portion is to compare the objective response rate (ORR) with historical rates for single agent trabectedin. Subjects from the Phase I portion of the trial who are treated at the dose ultimately used in the expansion will be included in the efficacy analysis. Our null hypothesis estimates the overall response rate of single agent trabectedin at 9.9%. We believe an increase in the response rate to 35% would be highly compelling. A total subject number of 22 gives us an 85% power to detect this increased response rate assuming a two-sided alpha of 0.05. 6 or more subjects with responses would suggest clinical activity of this regimen over single agent trabectedin.

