Early promising results in these Phase II studies led the European Organization for the Research and Treatment of Cancer (EORTC) to initiate a Phase II trial of trabectedin in 104 subjects treated in the second and third-line setting⁴⁵. This trial also reported a low response rate of 8%. The 6-month PFS was 29% and the median overall survival (OS) was reported as 9.2 months. Subsequently, a further Phase II trial in 36 subjects was run to evaluate the activity of trabectedin in the first-line setting. The overall response rate was reported as 17%, and the 1-year PFS and OS rates were 21% and 72%, respectively⁴⁶. This study also importantly concluded that trabectedin has similar ranges of objective responses and overall survival rates in the first-line setting to the two most active drugs in soft tissue sarcomas: doxorubicin and ifosfamide.

Demetri and colleagues performed a Phase II trial randomizing 270 subjects with leiomyosarcoma and liposarcoma to receive either 1.5mg/m² of trabectedin over 24 hours every 3 weeks, or 0.58 mg/m² over 3 hours every week for 3 out of 4 weeks⁴⁷. Subjects were required to have experienced documented disease progression while on doxorubicin and ifosfamide prior to trial entry. The 24-hour infusion schedule showed a significantly longer median time to progression (TTP) (3.7 vs. 2.3 months) and PFS at 6 months (3.3 vs. 2.3 months) as compared to the 3-hour infusion schedule. No significant difference in overall survival was observed between the two arms of the trial, however, there was a strong trend favoring the 24-hour infusion schedule (13.9 months vs. 11.8 months). Trabectedin was generally well tolerated in this study, with the most frequently reported grade 3/4 adverse events being neutropenia and elevated transaminases. Febrile neutropenia occurred in 1% of subjects, and the majority of adverse events were mild to moderate. There was also no documentation of cumulative toxicities. Another Phase II trial recommended the use of trabectedin as a neoadjuvant therapy for subjects with advanced myxoid liposarcoma⁴⁸.

The results of these Phase II trials led to licensing approval of trabectedin by the European Union for advanced soft tissue sarcoma in 2007, and the drug is now approved in over 70 countries.

Phase III and FDA Approval

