5.0 SUBJECT ELIGIBILITY

5.1 Inclusion criteria:

1. Subjects, ≥ 18 years old, must have a histologically confirmed diagnosis of advanced (metastatic or unresectable) soft tissue sarcoma with one of the following subtypes:
 - a. Leiomyosarcoma
 - b. Liposarcoma
2. Subject must be clinically indicated to receive trabectedin therapy as part of routine care. Subjects may be first line, or have received any number of prior systemic therapies.
3. Subjects must have adequate organ function and blood chemistry and blood count parameters as defined below. Transfusion is permitted as clinically indicated.
 - a. Total bilirubin ≤ 1.5 x upper limit of normal (ULN) mg/dL
 - b. AST ≤ 2.5 x ULN and ALT ≤ 2.5 x ULN
 - c. Alkaline Phosphatase < 2.5 x ULN
 - d. Serum creatinine ≤ 1.5 x ULN
 - e. Calculated creatinine clearance ≥ 30 mL/min using the Cockcroft-Gault formula may be included)
 - f. Creatinine phosphokinase (CPK) ≤ 2.5 x ULN
 - g. Absolute neutrophil count (ANC) $\geq 1.5 \times 10^9/L$;
 - h. Platelet count $\geq 100,000/mm^3$ ($100 \times 10^9/L$);
 - i. Hemoglobin ≥ 9 g/dL
4. Subjects must demonstrate a left ventricle ejection fraction (LVEF) of $> 45\%$ by ECHO or MUGA.
5. Male or non-pregnant and non-breast feeding female:
 - a. Females of child-bearing potential must agree to use highly effective contraception without interruption from initiation of therapy and while on study medication and have a negative serum pregnancy test (β - hCG) result at screening and agree to ongoing pregnancy testing during the course of the study, and at the end of study treatment. A highly effective method of contraception is defined as one that results in a low failure rate (that is, $< 1\%$ per year), when used consistently and correctly, such as implants, injectables, combined oral contraceptives, some intrauterine contraceptive devices, sexual abstinence, or a vasectomized partner (Appendix C).
 - b. Male subjects must practice abstinence or agree to use a condom during sexual contact with a pregnant female or a female of childbearing potential while participating in the study (Appendix C).
6. All ongoing toxicities related to prior therapies must be resolved to Grade 1 or better (except alopecia).
7. Subjects must have an ECOG performance status ≤ 1 or Karnofsky performance scale ≥ 70 (see Appendix A and B).
8. Subjects must have one or more measureable lesions, as determined by RECIST v1.1 assessed by CT or MRI.

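### Response rate is tested against one unsourced 9.9% trabectedin rate although first-line subjects are eligible without a cap, so six or seven responders may partly reflect line of therapy

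*Combined protocol and SAP*

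**What the plan says.** The synopsis names the type of control as historical. Section 16.3 sets the Phase II objective as to "compare the objective response rate (ORR) with historical rates for single agent trabectedin". The design values are:

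- Null: "Our null hypothesis estimates the overall response rate of single agent trabectedin at 9.9" percent.
- Alternative: "We believe an increase in the response rate to 35% would be highly compelling".
- Size and power: "A total subject number of 22 gives us an 85% power to detect this increased response rate assuming a two-sided alpha of 0.05".
- Decision rule: "6 or more subjects with responses would suggest clinical activity of this regimen over single agent trabectedin".

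Section 5.1, criterion 2, reads "Subject must be clinically indicated to receive trabectedin therapy as part of routine care" and continues "Subjects may be first line, or have received any number of prior systemic therapies". It sets no cap and no stratum.

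Section 2.6 gives these trabectedin response rates: 4% in 54 pretreated subjects, 8% in 36 previously treated subjects, and 8% in 104 subjects in second or third line. For a first-line trial in 36 subjects it says "The overall response rate was reported as 17" percent.

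Section 16 contains no line-specific reference rate, no adjustment or reporting by line of therapy, and no sensitivity analysis of the null. The regression described in 16.5 relates correlative measures to clinical outcome.

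**The concern.** Without a concurrent control, any statement about what avelumab adds rests on the reference rate fitting the subjects who enrol. The plan fixes that rate at one number. It also admits, in any proportion, a group for which its own background reports a rate well above that number. If many first-line subjects enrol, trabectedin alone would reach six responses more often than the design allows, and the rule could not tell an avelumab effect from a case-mix effect. This bears on the primary efficacy conclusion. If it is not settled in advance, any later correction for line of therapy would be open to dispute.

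**Working it through.** **Inputs.** N = 22, null 9.9%, alternative 35%, cutoff 6 and two-sided alpha 0.05 (0.025 in the upper tail), all from section 16.3. First-line rate 17%, from section 2.6. Rate in previously treated subjects: either 9.9% (the null read as a pretreated rate) or 8% (section 2.6); both are assumptions. Number of first-line subjects k: not given, so taken from 0 to 22.

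**Step 1: reproduce the plan.** With X ~ Bin(22, p), the exact tails P(X ≥ c) are:

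- p = 0.099: c = 5 gives 0.0600; c = 6 gives 0.0174.
- p = 0.35: c = 6 gives 0.837.

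Six is the smallest cutoff with an upper tail at or below 0.025. Exact power is 83.7% against the stated 85%; a normal approximation with continuity correction gives 84.6%. The stated design holds on its own assumptions.

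**Step 2: let the mix vary.** If avelumab adds nothing, X = Bin(k, 0.17) + Bin(22 − k, q), where q is the rate in previously treated subjects. The tail P(X ≥ 6) comes from convolving the two distributions:

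| First-line subjects k | q = 9.9% | q = 8% |
|---|---|---|
| 0 | 0.0174 | 0.0064 |
| 2 | 0.0229 | 0.0098 |
| 3 | 0.0261 | 0.0121 |
| 6 | 0.0376 | 0.0212 |
| 7 | 0.0421 | 0.0252 |
| 11 | 0.0641 | 0.0466 |
| 16 | 0.1007 | 0.0874 |
| 22 | 0.1576 | 0.1576 |

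The 0.025 tail is first exceeded at k = 3 (q = 9.9%) or k = 7 (q = 8%).

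**Step 3: where 9.9% would already be right.** With 8% and 17%, a mix reproduces 9.9% when the first-line share is (9.9 − 8)/(17 − 8) = 0.21, or about 4.6 of 22.

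**Step 4: cutoffs that follow the mix.** The smallest count with P(X ≥ c) ≤ 0.025 is:

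| Cutoff | k, with q = 9.9% | k, with q = 8% |
|---|---|---|
| 6 | 0–2 | 0–6 |
| 7 | 3–12 | 7–14 |
| 8 | 13–22 | 15–22 |

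**Step 5: what a higher primary cutoff would cost.** Power at 35% with N = 22 is 0.837 for cutoff 6, 0.698 for 7 and 0.526 for 8.

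**Step 6: how firm is 17%?** If it means 6 of 36 (an assumption), the exact 95% interval is about 6% to 33%, which includes 9.9%.

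**The case against.** The best defence has four parts.

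- **The line effect is not established.** Section 2.6 reports separate small trials, none comparing lines. Taking 6/36 for first line and 2/54 + 3/36 + 8/104 = 13/194 for pretreated subjects (counts inferred from the percentages), Fisher's exact test gives p = 0.09. This stands: 17% is imprecise. It is nevertheless the only first-line trabectedin response rate in the protocol.
- **The 17% is from a broader population.** The title of reference 46 describes chemotherapy-naive advanced soft tissue sarcoma, whereas this trial takes only leiomyosarcoma and liposarcoma. This stands too, but section 2.6 also describes the 4%, 8% and 8% trials as soft tissue sarcoma or sarcoma in general.
- **Few first-line subjects may enrol.** Trabectedin must be indicated as routine care, and section 2.1 names doxorubicin as standard front-line therapy. Both suggest a low share. Neither sets a limit, and criterion 2 expressly admits first line.
- **The null may already be a mix, or conservative.** All three pretreated figures lie below 9.9%. With 8% in previously treated subjects, the rule stays within 0.025 up to 6 first-line subjects. This stands, and it limits the size of the problem.

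A reader might infer that 9.9% is a pretreated rate, perhaps because the title of the Phase III trial (reference 17) refers to failure of conventional chemotherapy. The documents do not link 9.9% to that trial or give that trial's response rate. A reader might also infer a false-positive rate near 16%. That figure requires every subject to be first line.

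**Conclusion.** The concern holds in a limited form. The stated design is arithmetically sound for a population that truly responds to trabectedin at 9.9%. What is missing is a reason to think 9.9% fits the population that may enrol, and a plan for the case that it does not. The tail of the six-responder rule runs from 0.006 or 0.017 with no first-line subjects to 0.158 with all 22. It exceeds the nominal 0.025 from 3 or from 7 first-line subjects, depending on the rate in previously treated subjects. These figures rest on three assumptions: 17% in first line, 9.9% or 8% in the others, and an unknown first-line share.

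It might be inferred that the primary cutoff itself must be raised. The documents do not support going that far: one 36-subject estimate from a broader population is thin ground for cutting power at 35% from 84% to 70% or 53%. The point should be fixed, but it does not block the trial. It limits what a result of six or seven responders can be said to show.

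**What to change.** In section 16.3:

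1. State the source of the 9.9% and the line of therapy it represents.
2. Keep 9.9% and six or more responders as the primary rule.
3. Report the response rate by line (first line versus previously treated) beside the pooled rate.
4. Pre-specify a sensitivity analysis that compares the responder count with a reference rate weighted by the actual mix, using 17% for first line and, in turn, 9.9% and 8% for previously treated subjects.
5. Claim activity over single-agent trabectedin without qualification only if the count also meets the mix-weighted cutoff in step 4 of the working. The two versions differ only for 3–6 and 13–14 first-line subjects. There, a count that meets the lower cutoff but not the higher should be reported as depending on the reference rate.

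The cost is a wording change and a little more analysis. Medical history is already taken at screening (section 8.1), so line of therapy should be available. The drawback is that six or seven responders may carry a case-mix caveat if many first-line subjects enrol. Eligibility, N and the stated power are unchanged.
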